13.2 Laboratory Tests (Hematology, Serum Chemistry, Urinalysis, and PEth 16.0/18.1 (POPEth))

Summary statistics (n, mean, standard deviation, minimum, median, and maximum) will be presented for the observed values for hematology, serum chemistry, urinalysis, and PEth 16.0/18.1 (POPEth) at each time point for the safety population, as described in Section 5.2, Summarization of Data. Summary statistics will also be presented for the change-from-baseline values to each postbaseline time point. In these displays, baseline will be defined as the last non-missing value prior to first dose of study medication. Figures will be generated appropriate to the data output.

A shift table will be presented for baseline versus each post-baseline visit for absolute neutrophil count using following grades:

- Normal: ≥ 2.5 neutrophils (10**9/L);
- Grade 1: 1.5 to <2.5 neutrophils (10**9/L);
- Grade 2: 1.0 to <1.5 neutrophils (10**9/L);
- Grade 3: 0.5 to <1.0 neutrophils (10**9/L);
- Grade 4: <0.5 neutrophils (10**9/L)

Hematology, chemistry, urinalysis, and POPEth panel results will be listed, with values falling outside the laboratory reference range flagged.

Laboratory reference ranges will be provided by the laboratory site(s) and will be included in the clinical study report.

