5.2.2 Secondary Endpoints

Pharmacodynamics

- Change from baseline in body weight at Day 61.
- Change from baseline in whole body adiposity at Day 61.
- Changes from baseline in surrogate measures of liver inflammation and fibrosis at Day 61: Fibroscan[®] Vibration-controlled Transient Elastography (VCTE), Fibroscan[®] Controlled Attenuation Parameter (CAP) score, and Enhanced Liver Fibrosis (ELF) score.
- Change from baseline in lipid parameters and cardiovascular risk biomarkers at Day 61: serum high sensitivity C-reactive protein (hs-CRP), Lp(A), Apo B, low-density lipoprotein (LDL), high-density lipoprotein (HDL), total cholesterol, triglycerides, and free fatty acids (FFA).
- Change from baseline in metabolic disease parameters at Day 61: homeostatic model assessment for insulin resistance (HOMA-IR), fasting blood glucose concentrations, glycated albumin concentrations, HbA_{1c}.

Safety and Tolerability

- Summary of physical examinations findings over the course of the study.
- Adverse event (AE) assessment over the course of the study.
- Assessment of vital sign parameters over the course of the study. Parameters to include resting systolic and diastolic blood pressures, resting heart rates, resting respiratory rates, and oral body temperatures.
- Assessment of body weight over the course of the study.
- Safety 12-lead ECGs over the course of the study.
- Assessment of clinical laboratory values (hematology, full biochemistry panel (including lipid panel, CPK, magnesium, liver function tests) and urinalysis (UA) over 61 days of dosing.
- Assessment of ophthalmologic examination, including slit lamp, prior to and after 61 days of dosing.

Pharmacokinetics

- Population PK analysis of HU6 parent and metabolites, DNP and M1. The following PK parameters will be estimated as appropriate: C_{max}, T_{max}, t_{ν₂}, T_{lag}, AUC_{0-x}, CL/F, Vd/F, λ_z. Other PK parameters may be calculated, as data allow and appropriate.
- As data permit, noncompartmental analysis of HU6 parent and metabolites, DNP and M1. The following PK parameters will be calculated: C_{max}, AUC, and accumulation.
- Modeling of exposure response relationships of HU6, DNP and M1 and efficacy/pharmacodynamic endpoints, as appropriate.

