8.1 Schedule of Assessments

	Screening ^a	ng ^a Treatment Visits up											
	Visit 1	Vis	sit 2	Visit 3	Visit 4	Visit 5	Visit 6	Visit 7	Visit 8	Visit 9 ^b	Visit 10	10 Visit	
Activity/Day	Day-45 to - 3	Day 1: Predose	Day 1: Postdose	Day 2	Day 7	Day 14	Day 28	Day 42	Day 49	Day 61 ^b	Day 73	< 28 days of dosing	≥ 28 days of dosing
Visit Window					±1	±1	±4	±4	±2	varies ^b	±2		
Informed Consent	Х												
Inclusion / Exclusion Criteria	х	Х											
Medical History	х	Х											
Alcohol use assessment	Х												
Blood PEth Test	Х						Х						
TSH and T4	Х												
Serum triglycerides	Х												
HbA _{1c}	Х									Х		Х	х
Fibroscan	Х									Х		Х	Х
Demographics	Х												
eGFR (CKD-EPI)	Х												
Coagulation (INR)	Х												
Serology: HIV, HBsAg, HCV Ab	Х												
Urine Drug	Х	Х					Х			Х			
Urine Pregnancy test (female only)	Х	х			х	х	х	х		Х	Х	Х	Х
Laboratory U/A (dipstick)	х	х					х			Х	х	Х	Х
Hematology Panel (CBC)	х	х					х			Х	Х	Х	Х
Serum chemistry (includes LFTs)	х	Х					х			Х	Х	Х	Х

RIV-HU6-203 Version 1.0

	Screening ^a				Treatme	nt Visits					Follow- up		
	Visit 1	Vi	sit 2	Visit 3	Visit 4	Visit 5	Visit 6	Visit 7	Visit 8	Visit 9 ^b	Visit 10		ermination /isit
Activity/Day	Day-45 to - 3	Day 1: Predose	Day 1: Postdose	Day 2	Day 7	Day 14	Day 28	Day 42	Day 49	Day 61 ^b	Day 73	< 28 days of dosing	≥ 28 days of dosing
Visit Window					±1	±1	±4	±4	±2	varies ^b	±2		
Ophthalmologic exam	Х									Х			Х
Vital signs ^c and weight (InBody scale)	х	х	х	х	x	х	х	х	х	х	х	х	х
12-lead ECG	х	Х			х	Х	х	х		Х	Х	Х	х
Concomitant medications	Х	Х	Х	Х	х	х	х	х	Х	Х	Х	Х	Х
Adverse events	Х	Х	х	Х	х	х	х	х	Х	Х	Х	Х	Х
MRI/MRI-PDFF	Xď									Х			Х
Complete physical (includes neuro exam: muscle strength)	х									Х			х
Targeted physical (includes neuro exam: muscle strength)		х				х	х	х			х	х	
Glycated Albumin		х				х	х	х		Х		Х	Х
hs-CRP		Х					Х			Х			Х
Lipid Panel (HDL, LDL, VLDL, FFA, cholesterol, triglycerides)		Х					х			х			Х
ApoB and Lp(a)		Х					х			Х			Х
HOMA-IR: glucose, insulin, and C- peptide (3 draws 5 minutes apart)		х					х			х			Х
OWLiver (Metabolomics)		Х					х			Х			х
OWL (Lipidomics)		Х					х			Х			х
Proteomic Profile (SomaScan)		Х					х			Х			х

	Screening ^a Visit 1	Vi	sit 2	Visit 3	Treatme Visit 4	nt Visits Visit 5	Visit 6	Visit	Visit 8	Visit 9 ^b	Follow- up Visit 10	up /isit Early Termination		

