Urinalysis will consist of dipstick evaluations, with a reflex microscopic evaluation if dipstick shows blood or protein is small (1+), moderate (2+) or large (3+). Spot urine protein and albumin to be done if urine > trace protein on 2 collections.

Urine pregnancy tests will be conducted for female subjects.

Laboratory tests may be repeated once at screening. Additional laboratory evaluation may be performed at the discretion of the investigator in the assessment of an adverse event, as medically warranted.

11.6 12-lead Electrocardiogram

Refer to Section 8 for 12-lead ECG assessment time points.

Single 12-Lead ECG measurements will be obtained after the subject has rested in a supine position for at least 10 minutes. External stimuli should be kept to a minimum. Video games, watching of TV, and talking will not be allowed during this time. A digital ECG machine will be utilized for the trial. If an ECG timepoint coincides with any blood samples, the ECGs will performed \pm 10 minutes from obtaining the blood sample at the same timepoint. In addition, whenever possible, subjects should not have a meal within 2 hours prior to an ECG being performed.

The ECGs will be measured using an ECG machine that automatically calculates the heart rate and measures PR, RR, QRS, QT, and QTcF (Fridericia correction formula). The same ECG machine should be used for the same subject throughout the study, if at all possible. ECGs should be conducted in adherence with a research unit SOP acceptable to the Sponsor.

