4.2 Secondary Endpoints

Pharmacodynamics

• Change from baseline in body weight at Day 61.

- Change from baseline in whole body adiposity at Day 61 [i.e., total visceral adipose tissue (VAT) and subcutaneous adipose tissue (SAT)]
- Changes from baseline in surrogate measures of liver inflammation and fibrosis at Day 61: Fibroscan® Vibration-controlled Transient Elastography (VCTE), Fibroscan® Controlled Attenuation Parameter (CAP) score, and Enhanced Liver Fibrosis (ELF) score.
- Change from baseline in lipid parameters and cardiovascular risk biomarkers at Day 61: serum high sensitivity C-reactive protein (hs-CRP), Lp(A), Apo B, low-density lipoprotein (LDL), high-density lipoprotein (HDL), total cholesterol, triglycerides, and free fatty acids (FFA).
- Change from baseline in metabolic disease parameters at Day 61: homeostatic model assessment for insulin resistance (HOMA-IR), fasting blood glucose concentrations, glycated albumin concentrations, HbA_{1c}.

Safety and Tolerability

- Summary of physical examinations findings over the course of the study.
- Adverse event (AE) assessment over the course of the study.
- Assessment of vital sign parameters over the course of the study, including resting systolic and diastolic blood pressure, resting heart rate, resting respiratory rate, and oral body temperature.
- Assessment of body weight over the course of the study.
- Safety 12-lead electrocardiograms (ECGs) over the course of the study.
- Assessment of clinical laboratory values (hematology, full biochemistry panel (including lipid panel, creatinine phosphokinase (CPK), magnesium, liver function tests, and urinalysis over 61 days of dosing.
- Assessment of ophthalmologic examination, including slit lamp, prior to and after 61 days of dosing.

Pharmacokinetics

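### SAP 13.2 orders only continuous statistics for urinalysis, a graded dipstick, and does not carry over the protocol's rule of counts and percentages for categorical data

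*SAP*

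**What the plan says.** Urinalysis is part of a named safety endpoint in both documents: "urinalysis (UA) over 61 days of dosing" in protocol 5.2.2 and "liver function tests, and urinalysis over 61 days of dosing" in SAP 4.2.

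Protocol 11.5 says that urinalysis "will consist of dipstick evaluations, with a reflex microscopic evaluation if dipstick shows blood or protein is small (1+), moderate (2+) or large (3"; the last grade named is 3+. It adds a conditional follow-up: "Spot urine protein and albumin to be done if urine > trace protein on 2 collections". The schedule in protocol 8.1 also labels the test as a dipstick and places it at screening, Day 1 before dosing, Day 28, Day 61, Day 73 and early termination.

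For the analysis, SAP 13.2 says: "Summary statistics (n, mean, standard deviation, minimum, median, and maximum) will be presented for the observed values for hematology, serum chemistry, urinalysis", with PEth completing the list. It continues: "Summary statistics will also be presented for the change-from-baseline values to each postbaseline time point". The section's only categorical table is a neutrophil shift table. Urinalysis is also listed by subject, with out-of-range values flagged.

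Protocol 12.1 defines descriptive statistics by data type, with counts and percentages for categorical variables, unless something else is stated. Protocol 12.3.4 applies descriptive statistics to laboratory measures by treatment group and time point.

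**The concern.** A dipstick grade is an ordered category. It has no arithmetic mean, and the step from negative to 1+ is not known to equal the step from 1+ to 2+. Following SAP 13.2 literally means inventing codes for the grades, and the resulting mean, SD and mean change then depend on that choice.

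What is at stake is whether a reader of the study report can see how many subjects in each arm developed protein or blood in the urine. The protocol itself singles out these two findings for reflex microscopy and, for repeated proteinuria, for further urine testing. The natural by-arm result is a count at each grade, and the SAP does not ask for one.

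**Working it through.** The plan gives no figure of its own on this point, so the check compares the texts and then illustrates the consequence.

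**1. Type of data.** Protocol 11.5 gives grades for blood and protein. It does not list the other dipstick analytes. The conditional spot protein and albumin, and some microscopy items, may be numeric.

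**2. Statistics ordered.** SAP 13.2 names six continuous statistics for observed values and asks for summary statistics on change from baseline. It does not separate graded from numeric urine results and gives no coding.

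**3. Could other SAP text supply a categorical summary?** SAP 5.2 requires summaries by treatment group but has no rule for categorical data. Where the SAP wants counts, it says so:
- demographics (section 7);
- responder status (sections 11, 12 and 13.4);
- QTcF categories (13.5);
- the neutrophil shift table (13.2).

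Urinalysis is in none of these.

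**4. Illustration: the mean depends on the coding.** The grades and counts here are assumed; the arm size of 20 is from SAP section 2. Suppose 3 of 20 subjects in an HU6 arm go from negative to 2+ protein, the other 17 are unchanged, and nobody on placebo changes.
- Coding negative, trace, 1+, 2+, 3+ as 0, 1, 2, 3, 4: mean change = 3 × 3 / 20 = 0.45.
- Coding them as 0, 0.5, 1, 2, 3: mean change = 3 × 2 / 20 = 0.30.
- The median change is 0 under both, because 17 of 20 are unchanged.
- A count gives 3/20 = 15% against 0/20 = 0%, whatever the coding.

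**5. Illustration: one mean, two different pictures.** Code negative, 1+ and 2+ as 0, 1 and 2, in arms of 20.
- Four subjects at 1+, the rest negative: mean = 4 × 1 / 20 = 0.20, SD 0.41.
- Two subjects at 2+, the rest negative: mean = 2 × 2 / 20 = 0.20, SD 0.62.

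The means agree. The SD and the maximum (1 against 2) differ, but neither says how many subjects are affected. Counts would: 4/20 = 20% at 1+ in the first arm and 2/20 = 10% at 2+ in the second.

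**The case against.** The strongest reply is that the protocol already plans the right summary. Its definition of descriptive statistics covers categorical data, it applies to laboratory measures by treatment group, and the SAP nowhere says that it is departing from it. That stands as far as it goes: the fault lies in the SAP sentence, and the trial's plan as a whole does provide for counts. It does not rescue SAP 13.2, because the protocol's definition yields where something else is stated, and SAP 13.2 lists the continuous statistics by name. Programmers will work from that sentence.

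Three further points have weight.
- Clinically significant laboratory abnormalities that need active management are adverse events under protocol 11.7.1, and SAP 13.1 tabulates treatment-emergent events. This gives a by-arm route for the most important findings, but new 1+ or 2+ protein not judged to meet that bar would not enter those tables.
- Mean and change may be valid for urine items that are numeric, so the objection to continuous statistics is confined to graded results.
- In step 4 both codings give a positive mean change on HU6 against 0 on placebo, and the maximum would show the worst coded grade. The ordered statistics are poor for this purpose, but not wholly uninformative.

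A reader might also infer that negative results would be treated as missing and dropped, leaving only positives in the mean. The documents do not support this. The rules in protocol 12.4 and SAP 5.2 concern missing data, and a recorded negative is not missing. Nothing is said about positives being stored as numbers and negatives as text.

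**Conclusion.** The point holds as a small SAP correction. SAP 13.2 prescribes continuous statistics for a test that the protocol defines by grades, and specifies no valid by-arm summary for those grades. The remaining routes are the subject listings and, for abnormalities needing active management, the adverse event tables.

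A reader might go further and conclude that the urinalysis endpoint can have no valid comparison between arms at all. The documents do not support that, given the protocol's own rule for categorical data, the adverse event tables and the possibly numeric urine items.

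The size is limited to safety reporting in an exploratory study. The primary analysis, power and sample size are untouched. The conclusion rests on the text of protocol 11.5 and SAP 13.2. The figures in the working are illustrations on assumed counts and codings, not predictions.

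**What to change.** In SAP 13.2:
- limit mean, SD and the other continuous statistics, and change from baseline, to numeric urine parameters;
- for graded dipstick results, at least protein and blood, present n (%) by grade and arm at each scheduled visit;
- add a baseline-to-post-baseline shift table by arm for those results, in the format already specified for neutrophils. A column for the worst post-baseline grade is optional.

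This brings the SAP into line with protocol 12.1. The cost is a change of SAP wording and one table. No new data are needed, and no protocol procedure changes.

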11.5 Clinical Laboratory Tests

Refer to Section 8 for clinical laboratory blood and urine collection time points.

Refer to the Study Procedure Manual for more information about sample collection, processing, storage, and shipment.

At Screening only:

- Viral serology will include testing for the presence of hepatitis B antigen, anti-hepatitis C antibody and anti-HIV antibodies.
- TSH and Free T4.
- eGFR = CKD-EPI Creatinine Equation (NKF 2009; https://www.kidney.org/content/ckd-epicreatinine-equation-2009).

Hematology testing will include erythrocyte mean corpuscular hemoglobin concentration (MCHC), erythrocyte mean corpuscular volume (MCV), hematocrit, hemoglobin, leukocyte count, and absolute counts of lymphocytes, monocytes, neutrophils, basophils, eosinophils and platelets.

Serum chemistry analyses will include glucose, calcium, albumin, total protein, sodium, potassium, bicarbonate, chloride, magnesium, blood urea nitrogen (BUN), creatinine, alkaline phosphatase, phosphate, uric acid, lactate dehydrogenase, ALT, AST, gamma-glutamyl transferase (GGT), bilirubin (total and direct), amylase, and CPK.

• Baseline ALT and AST = while each value will be recorded, the average of screening and Day 1 predose values will be used as the baseline value in the statistical evaluation of these parameters in the exploratory analysis.

Lipid panel will include total cholesterol, HDL, LDL, VLDL, triglycerides, and FFA.

Additional tests at select time points include glycated albumin, hs-CRP, ApoB, Lp(a), and HOMA-IR (includes glucose, insulin, and C-peptide; Wallace 2004), and PEth test.

- For HOMA-IR, 3 blood samples for the 3 analytes (blood glucose, serum insulin, and C-peptide) will be drawn after a minimum of 5 minutes between each sample.
- The PEth test is a serum biomarker that can assess recent alcohol consumption. The value is dependent on both quantity of alcohol and time from consumption. This will be assessed at screening and Day 28. At the discretion of the investigator, it can be obtained at other times if there is concern for excessive alcohol consumption based on history, symptoms or laboratory evaluations (e.g. elevated liver function tests). The report lists several different assays, but this study will rely on the based on PEth 16.0/18.1 (POPEth) assay, which has been validated.

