4.3 Exploratory Endpoints

- Change from baseline in metabolomic and lipidomic profiles (One Way Liver-[OWL] metabolomic and lipidomic assays) at Day 61.
- Change from baseline in proteomic profiles (SomaScan®) at Day 61.
- Change from baseline in serum alanine aminotransferase (ALT) and aspartate aminotransferase (AST) concentrations at Day 61, as data allow.

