13.6 Lipidomic (OWL Metabolomics)

Lipidomic analyses are not described in this statistical analysis plan. A separate lipidomic analysis plan will be provided.

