13.7 Metabolomic (OWL Metabolomics)

Metabolomic analyses are not described in this statistical analysis plan. A separate metabolomic analysis plan will be provided.

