13.8 Proteomic (SomaScan® Assay)

Proteomic (SomaScan Assay) analyses are not described in this statistical analysis plan. A separate proteomic analysis plan will be provided.

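### Does the SAP put the exploratory Day 61 ALT/AST change on a different baseline from the one the Protocol sets?

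*SAP*

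**What the plan says.** Protocol 11.5 places ALT and AST in the serum chemistry panel ("lactate dehydrogenase, ALT, AST, gamma-glutamyl transferase (GGT"). It adds a rule for these two enzymes: each value is recorded, and "the average of screening and Day 1 predose values will be used as the baseline value in the statistical evaluation of these parameters". The sentence ends by limiting the rule to the exploratory analysis.

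SAP 4.3, like Protocol 5.2.3, lists the endpoint: "Change from baseline in serum alanine aminotransferase (ALT) and aspartate aminotransferase (AST) concentrations at Day 61, as data allow".

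SAP 13.2, under Safety Analyses and in the safety population, summarises serum chemistry at each time point and then says "Summary statistics will also be presented for the change-from-baseline values to each postbaseline time point". The baseline for those tables follows: "In these displays, baseline will be defined as the last non-missing value prior to first dose of study medication".

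No other SAP section takes up ALT or AST. In Section 12 they appear neither among the variables assessed only at Day 61 nor among the repeated-measures variables; the item called a liver panel there contains lipids only. The other three exploratory assay families are sent to separate plans: "Lipidomic analyses are not described in this statistical analysis plan", "Metabolomic analyses are not described in this statistical analysis plan" and "Proteomic (SomaScan Assay) analyses are not described in this statistical analysis plan". The revision entries in SAP Section 18 do not mention ALT or AST.

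**The concern.** A programmer working only from the SAP would find one instruction for ALT/AST change, the last-value rule in 13.2, and might take that table as the answer to the 4.3 endpoint. The reported change would then not be the one the Protocol defined, and the SAP would give no reason for it.

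For liver enzymes this is a fair thing to ask about. A single ALT reading is variable, and averaging two pre-treatment readings is a deliberate design choice. Losing it could alter each subject's change and the mean change within each arm. Two available baselines also leave room to choose between them after the data are seen.

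**Working it through.** The documents state no figure for ALT/AST variability or effect, so there is nothing to reproduce. The check has two parts: the scope of the two rules, and what the difference between them does.

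**Scope of each rule**

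| | Protocol 11.5 | SAP 13.2 |
|---|---|---|
| Variables | ALT and AST only | Hematology, serum chemistry, urinalysis, PEth |
| Use | Exploratory analysis | The safety displays in that section |
| Baseline | Mean of screening and Day 1 pre-dose | Last non-missing pre-dose value, normally Day 1 |

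The SAP nowhere calls the 13.2 table the analysis of the 4.3 endpoint. A last-value baseline is ordinary for a safety table. Both rules can be followed at once, so there is no contradiction, only an exploratory output that the SAP does not describe.

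**Difference for one subject**

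Let S be the screening value, D1 the Day 1 pre-dose value and D61 the Day 61 value. Protocol 8.1 schedules serum chemistry with liver function tests at all three.

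- Change on the 13.2 baseline: D61 − D1
- Change on the Protocol 11.5 baseline: D61 − (S + D1)/2
- Second minus first: (D1 − S)/2

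Hypothetical example, not trial data: D1 = 50 and D61 = 40 U/L give 40 − 50 = −10 (−20%) on the last value. With S = 60 the averaged baseline is 55 and the change is −15 (−27.3%). With S = 40 it is 45 and the change is −5 (−11.1%).

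**Difference for the treatment comparison**

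The extra term (D1 − S)/2 contains only pre-dose values. Under randomisation its expectation is the same in every arm, so it cancels:

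expected shift in the contrast = E[(D1 − S)/2 | HU6] − E[(D1 − S)/2 | placebo] = 0

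If screening values run d above Day 1 values on average, the mean change in every arm falls by d/2, placebo included. In one sample the two estimated contrasts would differ somewhat by chance, in either direction.

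**Precision**

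Take equal variances, set to 1, with correlations a (S, D1), b (D1, D61) and c (S, D61).

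- Var(last value) = 2 − 2b
- Var(averaged) = 1 + (1 + a)/2 − (b + c)

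The documents give no correlations, so these are assumed patterns:

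- All equal at 0.7: 0.60 against 0.45; SD ratio √(0.45/0.60) = 0.866, so averaging is 13% tighter.
- a = 0.8, b = 0.7, c = 0.5: 0.60 against 0.70; SD ratio √(0.70/0.60) = 1.080, so averaging is 8% looser.

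The sign depends on correlations that nobody has stated. These figures show only that neither baseline is reliably the more precise.

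**Can the Protocol's version still be produced?**

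Yes. Both pre-dose values are collected, and SAP 13.2 lists all chemistry results by subject. The derivation is one average per enzyme.

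**The case for a change.** The strongest reply is a dilemma. If 13.2 is meant to serve the 4.3 endpoint, it uses a baseline other than the Protocol's. If it is not, the endpoint has no output. Either way the SAP is incomplete. The as-data-allow qualifier does not help, because it concerns availability and both readings are scheduled. The SAP authors also wrote averaging down where they wanted it: HOMA-IR is the mean of three draws, and that choice is in the revision log. Finally, the Protocol rule leaves details open: which screening value counts after a permitted repeat test, what happens when one of the two values is missing under the no-imputation rule, and whether the FAS or the safety population applies.

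The second branch stands: the SAP names an endpoint and does not describe its summary. The first branch rests on reading the SAP's silence as a decision. Protocol 12.1 gives the SAP the role of adding statistical detail. Where it adds none, the Protocol definition remains in force, and reporting the endpoint from the last value would be a visible departure from it. That also limits the room for a choice after the fact. The open details are the kind an analyst settles when writing table specifications. They affect few subjects unless repeats or missing values are common, which the documents do not indicate.

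**Conclusion.** The observation is accurate as a gap in documentation, but no change to the plan follows. The two baseline rules apply to different outputs, and the 13.2 rule suits its purpose. The missing summary is one whose variables, time point and baseline the Protocol already fixes, from data already collected and listed.

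The size is (Day 1 − screening)/2 per subject, with zero expected shift in any HU6-placebo contrast and a precision effect of unknown sign. The endpoint is exploratory. It appears in neither the Protocol's nor the SAP's list of modelled variables, so no planned test turns on it. The MRI-PDFF analysis, the secondary efficacy and pharmacodynamic endpoints and the sample size are untouched.

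This rests on two assumptions: that randomisation and blinding hold up to the Day 1 pre-dose draw, and that whoever reports the exploratory endpoint reads Protocol 11.5 alongside the SAP. If the second failed, readers would see a conventional change from the last pre-dose value, which still gives a fair comparison between arms.
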